a) Change in medications that alter potassium homeostasis (e.g., RAAS inhibitors, diuretics, β -blockers) in the last month

b) Diagnosed with bowel diseases or syndromes (e.g., bowel obstruction, major GI surgery, short-bowel syndrome, irritable bowel syndrome, inflammatory bowel disease, chronic diarrhea)

c) Dietary restrictions (e.g., allergies) or otherwise unable/unwilling to adhere to study diets (excludes dietary restrictions on high-potassium foods)

d) Pregnant (females) or planning to become pregnant (males and females) during the study

If at any point during the study (including baseline) a participant has moderate-severe hyperkalemia (potassium \geq 6.5mEq/L), or if a participant becomes pregnant during the study, they will be withdrawn from the study.

Inclusion of women and minorities

Given the pilot nature of the intervention and small sample size (n=10), the study population will not be representative of the CKD population, and will have insufficient power to detect differences in intervention effects by sex and race/ethnicity. To our knowledge, plant-rich diets, such as those being investigated in this study, have similar health effects by sex and race/ethnicity. No individual will be excluded from the study on the basis of sex or race/ethnicity alone, and we will attempt to obtain a sample that reflects the demographics of our source population.

5) Study-Wide Number of Subjects

We will recruit a total of 10 individuals to the study. We have secured the support of the New York Harbor VA Healthcare System, which served approximately 250 non-dialysis CKD patients in the New York City area, as well as the Division of Nephrology at NYU Langone Health. It is estimated that approximately 10% of these patients have hyperkalemia. Thus, we have no concerns about our ability to access and recruit the required number of participants for this study. The estimate demographic breakdown of patients at the renal clinic are 95% male with 40% white, 25% black, 20% Hispanic, 10% Asian, and 5% other racial/ethnic background. The planned enrollment is outlined in Table 1.

Table 1. Planned enrollment report

Racial Categories	Ethnic Categories				Total
	Not Hispanic or Latino		Hispanic or Latino		
	Female	Male	Female	Male	
American Indian/ Alaskan Native	0	0	0	0	0
Asian	0	1	0	0	1
Native Hawaiian or Other Pacific Islander	0	0	0	0	0
Black or African American	0	2	0	1	3
White	1	3	0	1	5

More than 1 race	0	1	0	0	1
Total	1	7	0	2	10

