8) Study endpoints

Among 10 stages 3-4 CKD patients with persistent, mild hyperkalemia, we will evaluate, in a quasi-experimental, controlled feeding study, the efficacy of patiomer for maintaining normal serum potassium concentrations when following a plant-rich diet that includes high-potassium fruits and vegetables, as well as the effects of this diet on health outcomes. The participants will be transitioned gradually to a plant-rich diet, as outlined further below.

The interventions will be evaluated primarily in terms of serum potassium concentrations, but health outcomes will also be assessed, including blood pressure, gastrointestinal symptoms, and fasting concentrations of phosphorus, calcium, magnesium, albumin, glucose, insulin, cholesterol, LDL-cholesterol, HDL-cholesterol, triglycerides, urea nitrogen, bicarbonate and C-reactive protein. For all parameters, baseline values will be compared to values at the end of each diet phase (weeks 2 and 4).

9) **Procedures involved**

a. Design.

We will conduct an unblinded, quasi-experimental, controlled feeding study, which will be coordinated through the New York University – Health and Hospitals Corporation Clinical and Translational Science Institute (CTSI). Throughout the study, participants will be prescribed patiromer by the study nephrologist ([name]), which will be administered through the CTSI pharmacy. After a 1-week stabilization period, in which participants are prescribed Patiromer while following their usual diets, the feeding component of the study will occur in two phases. During the first phase (week 2), participants will be transitioned to a plant-rich renal diet, which contains moderate protein (10-15% of kcal), restricts dairy products (≤ 1 serving/day), and eliminates high-potassium fruits and vegetables. During the second phase (weeks 3 and 4), the diet will be altered to provide at-least half of fruits and vegetables from high-potassium sources. To reduce participant burden, meals will be delivered to participants by Portable Chef (New York, NY) three times per week.

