i. Patiromer. Patiromer dosing will be determined based on fasting potassium concentrations measured at the end of each week, factoring in both the absolute concentration, as well as the rate of change. The baseline dose of patiromer will correspond to the study by Weir et al. (2015); 8.4-g once per day for participants with a baseline serum potassium of ≥ 5.1 mEq/L. The following dosing schedule (Table 2) will be used for managing hyperkalemia during the study:

Table 2. Dosing of patiromer during the study based on serum potassium concentrations

Potassium	Change in Potassium	Action
<3.8 mEq/L	Same or decreased	Contact study nephrologist to determine dose
<3.8 mEq/L	Increased	Continue with current dose
3.8-5.0 mEq/L	Changed <0.5 mEq/L	Continue with current dose
3.8-5.0 mEq/L	Changed ≥ 0.5 mEq/L	Continue with current dose, but notify study nephrologist
5.1-6.0 mEq/L	Decreased	Continue with current dose
5.1-6.0 mEq/L	Same or increased	Contact study nephrologist to determine dose
>6.0 mEq/L	Decreased	Continue with current dose, but notify study nephrologist
>6.0 mEq/L	Same or increased	Contact study nephrologist to determine dose

ii. Research Diets. The guidelines for research diets are outlined in Table 3. With the exception of the Dairy Food Group, diets will be balanced according to the USDA MyPlate. Diets will be based on a 7-day menu cycle, and will be reviewed by participants during the screening visit. In order to promote participant adherence with the diets, participants will be permitted to select appropriate substitutes based on their food preferences from a list of pre-approved substitutes. For example, if a participant does not like to eat apples, they may substitute this for a list of other low-potassium fruits.

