iii. Serum potassium concentrations. The primary purpose of this study is to evaluate the efficacy of patiromer for maintaining serum potassium concentrations in CKD patients during transition to a liberalized plant-rich diet by comparing fasting serum potassium concentrations at screening to values at the end of phase I (week 2) and phase II (week 4) of the study. However, because potassium concentrations are also being used to titrate the dose of patiromer needed to achieve normal potassium concentrations, fasting serum potassium concentrations will also be measured at the end of weeks 1 and 3. To ensure a rapid response to changes in serum potassium concentrations, blood samples obtained at the CTSI CRC will be immediately delivered to the study laboratory at Tisch Hospital for analysis, and the results sent to the CTSI Pharmacy for evaluation (section 10.a.i.). Participants will be directed to pick up new prescriptions from the CTSI Pharmacy on the days of measurement. To obtain a measurement of serum potassium concentration, a 0.5 mL sample of blood is required.

iv. Blood pressure. Systolic and diastolic blood pressures will be measured after 5-minutes of rest in a seated position with their arm supported at the level of their heart and their feet resting on the floor using an automatic sphygmomanometer. Blood pressure measurements will be obtained in duplicate with a third measure obtained if the systolic or diastolic values on repeated measurement differ by more than 5 mmHg.

v. Gastrointestinal symptoms. The frequency and severity of participant gastrointestinal symptoms in the previous week (abdominal cramping, abdominal discomfort, indigestion, infrequent or difficult to pass bowel movements, flatulence, loose or watery stools) will be self-reported via an investigator-developed questionnaire at baseline, and at the end of the stabilization period (week 1), phase I diet (week 2), and phase II diet (week 4).

vi. Other biochemical parameters. Fasting blood samples will be obtained at the CTSI CRC, and analyzed for concentrations of phosphorus, calcium, magnesium, albumin, glucose, insulin, cholesterol, LDL-cholesterol, HDL-cholesterol, triglycerides, urea nitrogen, bicarbonate and C-reactive protein. Similar to serum potassium concentrations, blood samples will be delivered by study staff to the laboratory at Tisch Hospital for analysis. To obtain these biochemical measurements, approximately 5.0 mL of blood is required.

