A descriptive analysis of all data collected will be performed using appropriate graphical and numerical exploratory data techniques. The information obtained from this preliminary investigation of the data will be used to: (1) assess data quality and completeness, (2) describe univariate distributions at baseline and follow up, and (3) create summary statistical data for outcome variables at each time point, including the proportion of participants with hyperkalemia. We will identify features of the data that may necessitate special analytic methods (e.g., excess zeros, missing data, departures from distributional assumptions, outliers).

For analytic analyses, we will examine: (1) changes in outcome variables (blood pressure, gastrointestinal symptoms, and fasting concentrations of potassium, phosphorus, calcium, magnesium, albumin, glucose, insulin, cholesterol, LDL-cholesterol, HDL-cholesterol, triglycerides, urea nitrogen, bicarbonate and C-reactive protein), and covariates (weight, medications, dose of Patiromer) between baseline and the end of each diet phase, and (2) relationships between the changes in outcome variables and covariates. Changes in study outcomes will be graphically depicted using means \pm SD or median (IQR) as measures of central tendency and variance. Changes in study outcomes will be analyzed using repeated-measures analysis of variance with post-hoc Tukey HSD test. Because of the small sample size, covariates will be reported instead of being included in a multivariable model. Depending on the types of covariate and outcome of interest, subgroup analyses may be performed with these participants removed from the dataset. For example, if a participant's dose of phosphorus binder medications changed during the study, the analysis of phosphorus concentrations would be conducted with/without this participant. Given the short duration of this study (4 weeks) in relation to typical monitoring of patients with stage 3B-4 CKD, we expect that that few, if any, subgroup analyses will be required.

12) Provisions to Monitor the Data to Ensure the Safety of Subjects

Protection against Risk.

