Lastly, participants in the study are at risk of breaches of confidentiality. A variety of measures will be used to prevent breaches of confidentiality. First, all study staff will be trained in the NYULMC Practice Fundamentals, which include training in issues of confidentiality. Additionally, all study staff will be required to sign a confidentiality agreement. Although study staff may have access to sensitive information about the participant as recorded in their medical record, only that information pertinent to the study outcomes will be abstracted from the medical record. Data will be maintained as described above (see section 12). We will take steps to avoid participants' perceptions of coercion in the recruitment process.

13) Withdrawal of subjects

As mentioned previously, participants may be withdrawn from the study without their consent in the event that they become pregnant, or they are non-adherent with the research diets. Non-adherence to the research diets will be defined as consumption of >25% of energy from non-research diet foods, which will be assessed at the end of phase I of the study. In the event that involuntary withdrawal is required, participants will be referred back to their treating physician of record for evaluation and management. Data collection will cease at the time of withdrawal.

14) Risks to subjects

Most of the risks associated with this study are outlined in section 13 along with corresponding measures to protect against these risks (include hyperkalemia, patiromer side effects and interactions with medications, and breach of confidentiality). Blood tests will be drawn for this study, which are sometimes accompanied by bruising, bleeding, and minor tenderness at the puncture site. Participants will be made aware of all of these risks prior to enrolling in this study.

15) Potential Benefits of the Proposed Research to the Subjects and Others

Participants may experience some temporary improvement in cardiometabolic risk factors and serum potassium concentrations related to intervention; however, this is not guaranteed. Moreover, any temporary improvements in these conditions are unlikely to have any lasting benefits to participants.

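### Withdrawals for potassium ≥6.5 mEq/L before week 4 have no stated place in the week 4 result, and the planned analysis in its standard form omits them: a small effect, cheaply fixed by reporting

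*Combined protocol and SAP*

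**What the plan says.** - **Withdrawal rule.** Section 4 (after the exclusion criteria) opens the rule with "If at any point during the study (including baseline) a participant has moderate-severe hyperkalemia", sets the threshold at ≥6.5 mEq/L, and requires withdrawal.
- **After withdrawal.** Section 13: "Data collection will cease at the time of withdrawal". The reasons listed there are pregnancy and dietary non-adherence; the potassium threshold is not among them.
- **Primary comparison.** Section 9.b.iii compares screening potassium with weeks 2 and 4. For dose titration, "fasting serum potassium concentrations will also be measured at the end of weeks 1 and 3"; those two values lie outside the stated comparison.
- **Method.** Section 11.a: "Changes in study outcomes will be analyzed using repeated-measures analysis of variance", with Tukey post-hoc tests. It names missing data as something that might call for special methods but specifies none. It also promises the proportion with hyperkalemia at each time point, without a denominator.
- **Timing of the diets.** Section 9.a: "After a 1-week stabilization period, in which participants are prescribed Patiromer while following their usual diets", the two feeding phases follow. Week 1 potassium is therefore measured before any research diet.
- **Repeat testing.** Section 12 calls for another blood test when potassium is abnormally high or rising fast. It does not say whether withdrawal, or the analysis, uses the first or the repeat value.

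**The concern.** The study asks whether potassium can be kept normal. The ≥6.5 rule removes the participants in whom control failed most plainly, so this missingness depends on the primary outcome. Such a participant has no week 4 value, and repeated-measures ANOVA in its usual form discards the whole row. A triggering value from week 1 or 3 was measured but is not in the stated comparison at all. A week 2 trigger gives a usable value that is lost for want of week 4. A trigger at week 4 itself leaves complete data and causes no problem.

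What remains at week 4 is a group selected for not having failed badly. Section 2 makes a later randomized trial conditional on success here, so the reader should be able to see the week 4 result with and without these participants. If no rule is written beforehand, the denominator can be chosen after the results are known.

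**Working it through.** The plan gives n = 10 and no SD, effect size, event rate or dropout rate, so there is no stated figure to reproduce. From the documents: n = 10, entry range 5.1 to <6.5, withdrawal at ≥6.5, hyperkalemia taken as ≥5.1 mEq/L. Everything else below is assumed.

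**Scenario set A.** Normal values with equal within-person correlation (0.3 to 0.7) and SD 0.4 to 0.6. Withdrawal is at the first week 1 to 3 value ≥6.5. Means for screening and weeks 1 to 4 are:
- fall: 5.4/5.1/5.0/4.9/4.9
- flat: 5.4/5.2/5.3/5.4/5.4
- rise: 5.4/5.2/5.4/5.7/5.7

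These means apply before the entry range is imposed. Enrolled participants average about 5.55 to 5.65 at screening.

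Let p be the risk of withdrawal before week 4 and c the proportion of completers with potassium ≥5.1 at week 4.

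| | Fall | Flat | Rise |
|---|---|---|---|
| p, single value | 0.0003–0.0224 | 0.0044–0.0773 | 0.029–0.149 |
| At least one in 10: 1 − (1 − p)^10 | 0–20% | 4–55% | 25–80% |
| Same, if an independent repeat must also be ≥6.5 | 0–2% | 0–12% | 3–37% |
| c | 35–47% | 73–88% | 86–98% |
| Average gap in proportion: p(1 − c) | 0.0–1.3 points | 0.1–2.1 | 0.1–2.0 |
| Shift from one withdrawal: (1 − c)/10 | 5.3–6.5 points | 1.2–2.7 | 0.2–1.4 |
| Average bias in mean change (mEq/L) | 0.000 to −0.005 | −0.001 to −0.016 | −0.002 to −0.029 |
| Share of triggers at week 1 | 51–73% | 11–23% | 2–12% |

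Worked case (flat, SD 0.6, correlation 0.3): p = 0.0773 and c = 72.8%, so the gap is 0.0773 × 0.272 = 2.1 points, or 72.8% against 74.9%. With the independent repeat, the average gap is at most 0.4 points and the mean bias at most 0.010 mEq/L. Dose response to an individual's value is not modelled.

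**Scenario set B.** Screening mean 5.4 (SD 0.25, held within the entry range). Week 1 to 4 means are 4.8/4.6/4.7/4.7, 5.0/4.9/5.0/5.0 or 5.2/5.1/5.3/5.3, with between-person SD 0.3 to 0.6 and within-person SD 0.3 to 0.4. The average bias in mean change is 0.000 to 0.084 mEq/L. It can exceed set A because screening is drawn independently of the person's later level, so a high personal level does not cancel in the change.

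**Mean change when a withdrawal occurs.** Against the value the person would have had at week 4, the shift is roughly 0.01 to 0.03 mEq/L in set A and 0.07 to 0.15 in set B. In set B it is 0.14 to 0.22 if the triggering value is carried forward, against a sampling SD of the mean change of 0.15 to 0.24. A hand check of the carried version: nine completers averaging 4.6 and one withdrawal at 6.5 give (9 × 4.6 + 6.5)/10 = 4.79, a shift of 0.19.

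**Illustration with exact 95% intervals.** 3/9 = 33% (7.5–70%) for completers becomes 4/10 = 40% (12–74%) when one withdrawal counts as a failure. The largest possible shift is 0/9 to 1/10, which is 10 points. With c at its lowest (about 35%), the chance of 0/9 is 0.65^9 ≈ 2%, so this is an arithmetic ceiling and not an expected result.

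**Mixed model.** In a check at n = 10 (SD 0.6, single value), completer bias was −0.004 to −0.030 mEq/L and mixed-model bias +0.001 to +0.011. That check used screening as a covariate. The version proposed under the fix treats screening as an outcome and was not simulated separately.

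**The case against.** The strongest reply is that the numbers are small. Where control succeeds (fall), the average bias is at most 0.005 mEq/L and a withdrawal is unlikely. The larger average figures in set A arise in the flat and rise scenarios, where 73 to 98% of completers are hyperkalemic at week 4 and the study would look unsuccessful under either analysis. This stands, and it is why the point is minor.

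A second reply is that the protocol nowhere prescribes deletion. Section 11.a leaves room for special methods for missing data, and a mixed model would keep partial records. That also stands: the dropping follows from the standard form of the named method. But leaving room is not a rule, and the one with/without example given there concerns a change in binder dose, not outcome-driven withdrawal.

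A reader might infer that the plan conceals its failures. The documents do not support that. Section 11.a describes the proportion with hyperkalemia at each time point, and section 12 has the principal investigator review moderate-severe episodes at mid-enrolment. What is missing is any link from those events to the week 4 result. A reader might also count every such withdrawal as a failure of the plant-rich diet, but week 1 triggers occur on the usual diet.

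**Conclusion.** The point holds as a minor one. Followed as written and fitted in the standard way, the plan leaves participants withdrawn for potassium ≥6.5 mEq/L at weeks 1 to 3 out of the week 4 comparison, which tilts it towards apparent success. The average tilt is small under every assumption tried, and smaller still if withdrawal requires a confirmed value. In a single trial of 10, one such event can be noticeable: several percentage points when most completers are controlled, and in set B a shift in mean change approaching its sampling SD.

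It would be tempting to conclude that the omission could reverse the decision on a randomized trial. Nothing in the documents supports that: they give no event rate, SD or success threshold, and the modelled effects are too small to carry such a claim. The direction follows from the rules themselves; the size depends wholly on the assumed means, SDs and correlations.

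**What to change.** Amend section 11.a as follows.

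1. Beside the week 4 result, report the number and timing of withdrawals for potassium ≥6.5 mEq/L, with week 1 triggers shown separately.
2. Report the week 4 proportion with potassium ≥5.1 mEq/L, with exact confidence intervals, in two ways: completers only, and all who started patiromer with the ≥6.5 withdrawals counted as failures. Give the second figure with and without week 1 triggers. List withdrawals for non-adherence, pregnancy or other reasons separately, and state their place in the denominator.
3. As a supporting analysis of mean potassium, fit a mixed model with screening and all weekly values, including the triggering value, as repeated outcomes and time as a categorical factor. Report the screening-to-week-2 and screening-to-week-4 contrasts beside the planned ANOVA. State whether the original or the confirmatory value is analysed.
4. Reconcile sections 4, 12 and 13 on the reasons for withdrawal and on which potassium value triggers it. How these are settled is for the investigators.

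The cost is protocol wording and slightly more analysis work, with no added visits or blood tests. The reported control rate may come out lower, and at n = 10 the mixed model should be expected to reduce the bias, not remove it.

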Renal Clinic at the New York Harbor Veterans Affairs Healthcare System: The Renal Clinic at the New York Harbor VA Healthcare System serves approximately 250 CKD patients in the Greater New York City region, and will be the source population for this study. The electronic medical records system at the New York VA Healthcare System will be used to assist in identifying potentially eligible patients for the study, and for obtaining clinical information to describe the patient population.

Department of Population Health, NYULMC: The Department of Population Health, within NYUSOM, aims to integrate, support, and advance NYULMC's contributions to population health research and related disciplines, providing a vibrant departmental home for the "bedside-to-population" as well as the "population-to-discovery" domains of translational research. It provides an academic base for efforts to integrate research into NYU's expanding health care delivery system that transcends any particular school, department, or division. The Department is a research and training hub that brings together researchers in nursing, medicine, psychology, epidemiology, biostatistics, health services and policy, behavior change, comparative effectiveness, medical ethics, prevention, and related disciplines, affording a unique and collaborative environment focused on improving the health of populations. The Department was initiated in January 2012. A core focus of the Department is improving health outcomes through innovative interventions as well as in enhancing the impact of interventions already known to be effective through their more effective implementation and dissemination. Collaboration with key public sector stakeholders and with community partners is central to the Department's mission. As researchers, faculty are engaged in dual roles: building cutting-edge science in their areas of inquiry, and providing collaborative consultation to other investigators throughout the NYULMC academic community as well as across the University. Resources within the Department for this proposal include the use of over 5,000 square feet of dedicated office space located on the newly renovated 6th floor of the NYULMC Translational Research Building, telecom (phone, fax and LAN connections), administrative assistants, and grant, regulatory (IRB) and finance administrators.

Center for Healthful Behavior Change, NYULMC: The Center for Healthful Behavior Change (CHBC) is located within the Department of Population Health. The mission of CHBC is to become a national leader in translational behavioral medicine, research, training, and education. The CHBC works toward this mission through the development, implementation, and dissemination of innovative evidence-based behavioral interventions in routine clinical practice and community-based settings with the long-term goal of disseminating effective strategies nationally and internationally. The Center is comprised of core research faculty members with expertise in various fields relevant to translational behavioral research. Faculty engage in research pertaining to heart disease, hypertension, chronic kidney disease, diabetes, cancer, health disparities research, community-based participatory research, health psychology, behavioral informatics, and health education and counseling.

Division of Biostatistics NYULMC: [name] office is [name], in the same building as the study coordinator ([name]). [name] has access to state-of-the-art computing facilities that include a central server (Dell PowerEdge 2500) and a Sun Server. Statistical software available either on the network or the

desktop includes SAS, SPSS, S-Plus (including Spatial Stats and Environmental Statistics Modules), R, PASS and Matlab.

Portable Chef: Portable Chef is a metabolic kitchen / foodservice vender that will carry out the critical task of preparing meals and snacks for the study. This responsibility includes developing menus based on the pre-defined dietary patterns, sourcing ingredients, preparing and weighing foods and beverages, and delivering them to the participants to consume. The project study dietitian ([name]) reviewed available foodservice operations in the Greater New York City area, and selected Portable Chef for this intervention based on their capacity, delivery, and experience in developing and preparing tailored, weighed menus for researchers and clients with special food requirements.

22) **Prior approvals**

We have received approval from the Chief of the Nephrology at the New York Harbor VA Healthcare System to coordinate this study in their Renal Clinic. We also have approval from Portable Chef Director ([name]), and a vendor agreement with Portable Chef is already in place for prior research projects.

23) **Subject Payments**

Potential participants will be paid \$25.00 for the screening visit, and enrolled participants will additionally receive \$25.00 per visit to the CTSI CRC.

24) **Local number of subjects**

We will recruit a total of 10 individuals to the study. Preliminary data from the New York Harbor VA Healthcare System indicate that we will have access to approximately 250 patients with CKD, ~10% of which have hyperkalemia.

25) **Confidentiality**

Some of the participant data such as laboratory results will be linked to the participant's name in their medical chart. Other data (e.g., surveys) will be linked to the participant through an ID number. We will maintain separate files for identified and de-identified data in locked file cabinets in a locked office. Access to these data will be restricted to the PI ([name]), and study staff responsible for gathering data and maintaining research files. Data will be entered into a centralized database maintained on a secure server. Data in these files will be linked to participants only through their ID number. All data collected will be used expressly for the purpose of the proposed study.

26) **Provisions to Protect the Privacy Interests of Subjects**

Measures to be used to protect subjects' privacy interests are described in section 13 above. Data collection will occur at the New York Harbor VA Healthcare System (for medical chart review), CTSI Pharmacy (for patiomer dose), and CTSI CRC (questionnaires, anthropometric and clinical measurements, blood tests). Measurements at the CTSI will be conducted in private rooms. Participants will be told that they can refuse to respond to any questions that make them uncomfortable, and that they can withdraw from the study at any time.

27) **Compensation for research-related injury**

Participants will not be compensated for research-related injuries.

28) **Economic burden to subjects**

Neither the patient nor the patient's health insurance will be billed for any study activities (including research diets), tests, or procedures related to the study. The cost of all procedures and tests will be covered by funds

received from Relypsa, Inc.

29) Consent process

A brief description of the study will be provided at the time of screening for the study. After reviewing the consent form with patients, and after they have signed the consent form, we will verify that they meet the inclusion/exclusion criteria (sections 5.i and 5.ii.). Potential participants will be shown the research diet menus to determine whether they are willing and able to adhere to the research diets. All questions will be answered.

A copy of the consent form will be given to the participant and they will be encouraged to contact the PIs with any and all questions that occur at any time during the conduct of the study. No patients will be excluded on the basis of race/ethnicity, but this pilot study has a sample size that is insufficient to examine differences in the intervention by race/ethnicity.

30) Process to document consent in writing

Patient's consented participation in this study will be documented in their medical record.

31) Drugs or devices

Participants in this study will be prescribed patiromer (dosing 10.a.i. Table 2), under the supervision of the study nephrologist ([name]). Patiromer is an FDA-approved cation-exchange polymer that binds to potassium in the digestive tract, and is excreted (along with bound potassium) in feces. Patiromer is indicated for the treatment of hyperkalemia, and is demonstrated to result in clinically significant reductions in serum potassium concentrations. The safety concerns associated with patiromer, along with measures to reduce these complications, are noted in section 13, and include constipation (7.2%), hypomagnesemia (5.3%), diarrhea (4.8%), nausea (4.8%), abdominal discomfort (2.0%) and flatulence (2.0%), and binding to other medications.

References.

1. United States Renal Data System. 2016 USRDS annual data report: Epidemiology of kidney disease in the United States. National Institutes of Health, National Institute of Diabetes and Digestive and Kidney Diseases, Bethesda, MD, 2016.
4. St-Jules DE, [name] DS, Sevick MA. Nutrient non-equivalence: Does restricting high-potassium plant foods help to prevent hyperkalemia in hemodialysis patients? *J Ren Nutr* 2016;26(5):282-287.
